#### **B.1.2 HCA Healthcare Infrastructure for the INSPIRE-ASP Intervention Arm**

HCA Healthcare currently requires physicians to provide an indication when an antibiotic is ordered (see **Appendix B** for example CPOE indication screens). For facilities assigned to the intervention arm of the INSPIRE-ASP Pneumonia Trial, an INSPIRE CPOE smart prompt will be triggered when physicians prescribe an extended-spectrum (ES, **Table 1**) for a

pneumonia indication in the first three days of a hospital stay. This CPOE smart prompt will provide clinicians with a patient-specific estimate of the likelihood that the pneumonia is due to the associated target pathogens (e.g. MRSA, *Pseudomonas*, ESBL, or CRE, **Table 1**). The smart prompt will also provide guidance for appropriate empiric antibiotic options per trial protocol and hospital policy.

For example, if an anti-MRSA antibiotic is being ordered for pneumonia, the clinician will receive a prompt during the ordering process providing the probability that the patient has pneumonia due to MRSA. Recommendations for using standard-spectrum antibiotics (e.g. ceftriaxone) will be made when the probability of a given MDRO is lower than a given threshold (e.g., <10%). This threshold used in the trial will be finalized after evaluation of the prevalence of MDROs, and after discussion with the INSPIRE-ASP Steering Committee. Similarly, if an ES antibiotic is selected that targets a resistant Gram-negative *Enterobacteriaceae* or *Pseudomonas aeruginosa*, the ordering physician will receive information on the probability that the patient is likely to grow such organisms. The smart prompt will account for personal attributes of the patient as well as local resistance patterns. Hospitals randomized to routine care will continue their baseline stewardship activities, principally involving a decision support tool known as Rx VigiLanz Therapeutic Advisor, which has been adopted by all HCA hospitals. This tool alerts stewardship teams of possible opportunities for intervention, based on microbiology results. Intervention hospitals will also continue these activities.

The study population is defined at the hospital level, where the intervention will be adopted as part of a hospital-wide antibiotic stewardship quality improvement initiative targeting non-ICU adult patients admitted with pneumonia. Hospitals eligibility criteria are outlined in **Section B.1.3**.

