The primary trial analysis will use an as-randomized unadjusted model with two-tailed significance set at alpha = 0.05. Secondary outcomes also will be assessed using an as-randomized unadjusted model with adjustment for multiple comparisons with two-tailed significance set at alpha = 0.025 for the two secondary outcomes. Subsequent analyses of the primary and secondary outcomes will include both as-treated and adjusted models. Adjusted models will account for individual characteristics such as age, gender, comorbidities, and prior history of MDROs as well as hospital characteristics such as hospital antibiotic resistance. We will also account for randomization unit and for seasonality. These analyses will be reported as point estimates with confidence intervals without p-value. The reason for including these analyses is to provide additional information related to the trial outcomes for readers to assess the effects of potential confounders. The reason to not include them in a formal multiple comparisons adjustment is because these analyses are non-independent evaluations relative to the as-randomized unadjusted analyses.

Safety outcomes noted in the above table will be assessed in the most conservative manner to identify potential safety issues. This is required because a reduction in ES-DOT might be achieved only by incorrectly withholding ES antibiotics when they were really needed. Each safety outcome will be evaluated for non-inferiority using an as-randomized unadjusted model with a one-tailed significance set at alpha = 0.05. Analyses planned for these assessments are proportional hazards models with random effects (to account for hospital effects). These models are sometimes called frailty or shared frailty models. Because these are safety outcomes, we do not intend to make adjustments for multiple comparisons in testing them, further increasing conservatism.

All analyses will be performed using current versions of SAS (Version 9.4, as of writing, SAS Institute, Cary NC) and/or R (Version 4.0, as of writing).

Power Size/Sample Size Calculations

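### Safety non-inferiority is tested only as-randomized, in a cohort wider than the admissions the prompt can affect, so the claim of maximal conservatism is not supported

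*SAP*

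**What the plan says.** The SAP (Primary Statistical Analysis) states for safety: "Each safety outcome will be evaluated for non-inferiority using an as-randomized unadjusted model", "with a one-tailed significance set at alpha = 0.05", fitted as proportional hazards models with hospital random effects. It introduces this by saying that the outcomes "will be assessed in the most conservative manner to identify potential safety issues", and gives the reason: "a reduction in ES-DOT might be achieved only by incorrectly withholding ES antibiotics when they were really needed". Protocol B.1.10 carries the same plan.

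For effectiveness the SAP goes further: "Subsequent analyses of the primary and secondary outcomes will include both as-treated and adjusted models". The safety outcomes are not in that group. Protocol Table 4 and SAP Table 2 list them separately, as other pre-specified outcomes: antibacterial escalation, ICU transfer and length of stay.

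The analysis cohort is adult admissions to a non-ICU location with a present-on-admission pneumonia code and any antibiotic in the first three days. Protocol B.1.1 accepts a primary or a secondary code. The intervention reaches fewer admissions than that. Protocol B.1.2 says "an INSPIRE CPOE smart prompt will be triggered when physicians prescribe an extended-spectrum" drug for pneumonia in those three days. The SAP Background limits the standard-spectrum recommendation to an estimated risk below 10%. Protocol B.1.4 leaves the decision to the physician, and B.1.8 provides for reporting why prescribers stayed with extended-spectrum therapy.

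**The concern.** The harm the plan names, withholding an extended-spectrum drug that was needed, can arise only where treatment actually changes. Admissions with unchanged treatment add no information about that harm, yet they count in the safety comparison. In a superiority test such dilution works against the sponsor's claim. In a non-inferiority test it works for the claim. The plan gives supportive analyses to the effectiveness outcomes and none to safety, while presenting the safety approach as the most cautious available. At stake is whether a statement that the prompt is safe says anything about the patients whose antibiotics it altered.

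**Working it through.** The plan states no figure for any safety outcome, so there is none to reproduce. Its 97% power (CI 91-99%) is for ES-DOT and comes from a bootstrap of hospital data that the documents do not contain. The check is therefore a comparison of sections plus one line of algebra for direction.

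**1. Analyses planned, by outcome class**

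| Outcome class | As-randomized, unadjusted | As-treated | Supportive subset the prompt can affect |
|---|---|---|---|
| Primary and secondary | Yes | Yes (term not defined) | None named |
| Safety | Yes (only analysis) | No | None named |

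**2. Cohort against reach of the prompt.** Treatment changes through the prompt only if three conditions hold: an extended-spectrum order is placed for pneumonia within three days, the estimated risk is below the threshold, and the prescriber accepts the recommendation. The cohort requires none of these.

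**3. Direction, for ICU transfer and length of stay.** Let f be the share of intervention-arm admissions whose treatment changes. Let d(t) be the average change, in those admissions, in the probability of the event by day t. Assume no effect where treatment is unchanged. The arm-level change is then

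D(t) = f × d(t) + (1 − f) × 0 = f × d(t).

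For any f between 0 and 1, |D(t)| < |d(t)|. For ICU transfer, harm is d(t) > 0. For length of stay the event is discharge, so harm is d(t) < 0. In both cases the arm contrast lies closer to no difference than the contrast among changed admissions. Non-inferiority is declared when the harm-side confidence bound falls inside the margin, so a shift toward no difference makes that declaration easier. The frailty model reports a hazard ratio rather than a difference in risk, so this gives the direction and not the size on the model's scale.

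**4. Escalation.** The clock starts at the first standard-spectrum drug and stops at a switch to an extended-spectrum one. The risk set is admissions that received standard-spectrum therapy, not the whole cohort. The intervention aims to move admissions from extended- to standard-spectrum starts, so it can change who is in that set. The arms are then compared on groups formed after randomization. The documents do not show whether the added admissions would raise or lower the escalation rate, so this bias cannot be signed.

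**5. Inputs needed for a size.** The share f, the override rate, the event rates and the non-inferiority margin are all needed. None is stated in either document.

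**6. The other feature offered as conservative.** The SAP says "we do not intend to make adjustments for multiple comparisons in testing them, further increasing conservatism". That concerns error rates across the three tests and does nothing about dilution.

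**The case against.** The strongest reply is that the intervention is a hospital-wide strategy. Hospitals are randomized, and the as-randomized contrast estimates the effect of adopting the policy while preserving randomization. That stands, and it is why this analysis should remain the main safety test.

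Second, a patient-level as-treated analysis is not automatically more cautious. If prescribers override the prompt for sicker patients, the changed patients are the healthier ones and harm could be hidden. The term is also undefined in both documents. That stands too, and it rules out selecting on prescriber response.

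Third, covariate adjustment does not undo dilution from unaffected admissions, so the absence of adjusted safety models is no part of this point.

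Two stronger readings are tempting.

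- A reader might infer from the 12.5% target for ES-DOT that only a small share of patients change, so that harm would almost vanish. The documents do not support this, because ES-DOT counts drug-days. Assume equal use across recipients. If each changed patient loses all extended-spectrum therapy, 12.5% ÷ 1 = 12.5% of recipients change. If each is on two drugs for three days (six drug-days) and loses one drug-day, 12.5% ÷ (1/6) = 75% change. The plan's power simulation also reduces therapy in every intervention admission rather than in a subset.
- A reader might infer that as-randomized is the worst available choice, or that the test could not have shown harm. Either would need the share changed, the margin and the event counts, which are not given.

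**Conclusion.** The point holds in a limited form and warrants a change to the SAP. For ICU transfer and length of stay, the only planned safety analysis pulls harm among changed admissions toward no difference and so favours a finding of non-inferiority. The direction follows from the trigger, the risk threshold and the freedom to override, given no effect where treatment is unchanged. The size cannot be determined from the documents. For escalation the problem is post-randomization selection into the risk set, with unknown direction. The as-randomized test remains a valid estimate of the policy effect. What fails is leaving it alone, without a supportive analysis, and describing it as the most cautious option.

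**What to change.** 1. Keep the as-randomized frailty models as the main safety test.
2. Pre-specify a supportive run of the same models in cohort admissions whose algorithm-estimated MDRO risk is below the trial threshold. Compute the risk retrospectively and identically in both arms, and do not select on whether the prescriber accepted the prompt. State how the pathogen-specific estimates combine into one definition of low risk, and report the size of the subset by arm.
3. Extend the as-treated analysis already planned for effectiveness to the safety outcomes as a further sensitivity analysis, with treatment status defined at hospital level.
4. Require that a conclusion of safety be consistent across these analyses.
5. State that the escalation risk set is formed after randomization, and interpret that outcome accordingly. The low-risk run does not cure this.
6. Remove or correct the claim of conservatism for the as-randomized-only test.

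The cost is a little more analysis work and wider intervals in the subset. Hospital-level as-treated status also gives up part of the protection of randomization, so it supports the main result and does not replace it. The subset reduces dilution without removing it: it still holds admissions with no extended-spectrum order and those where the prompt was overridden. The resistance risks cited in Protocol A.1.4 (at most 4.6% for any listed organism) are below 10%, so the subset may hold most of the cohort.

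One feasibility point must be confirmed. Antibiotic orders already require an indication, and MDRO history is already planned for the adjusted models, but the documents do not say that the full risk score can be computed for routine-care admissions.

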**Table 4: Other Pre-Specified Outcomes – Safety Trial Outcomes**

Safety Trial Outcomes (other pre-specified outcomes)	
Antibacterial Escalations [Safety Outcome]	Days from start of standard-spectrum antibacterial until switch to extended-spectrum antibacterial during hospital stay
ICU Transfers [Safety Outcome]	Days from start of hospitalization until ICU transfer within hospital stay
Length-of-stay [Safety Outcome]	Days from hospital admission to discharge

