Vancomycin Days of Antibacterial Therapy per Empiric Day	The summed number of days of Vancomycin received each empiric day per at-risk-day (first 3 days of admission) ¹		
Antipseudomonal Antibiotic Days Of Therapy (ES-DOT) per Empiric Day	The summed number of different antipseudomonal antibacterials received each empiric day, measured repeatedly over the first three days of an admission and divided by the number of empiric days of the admission. An empiric day is a day within the first three days of an admission. ^{1,2}		

¹E.g., if a patient is admitted for 2 days, ES-DOT will be calculated for 2 days and divided by 2 empiric days; conversely if a patient is admitted for 4 days, only the first 3 days will be evaluated.

²Does not include aminoglycosides or fluoroquinolones.

Safety outcomes planned for the primary manuscript are shown in Table 2. Safety outcomes will be analyzed separately from the main effectiveness outcomes of the trial (see Primary Statistical Analysis section below).

Table 2: Other Pre-Specified Outcomes – Safety Trial Outcomes

Safety Trial Outcomes (other pre-specified outcomes)	
Antibacterial Escalations [Safety	Days from start of standard-spectrum antibacterial until switch to extended-
Outcome]	spectrum antibacterial during hospital stay
ICU Transfers [Safety Outcome]	Days from start of hospitalization until ICU transfer within hospital stay
Length-of-stay [Safety Outcome]	Days from hospital admission to discharge

Primary Statistical Analysis

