The unit of analysis will be individual admissions. Individuals can contribute more than one admission. The analytic model will be a generalized linear mixed effects model for differences in differences, with random effects accounting for correlation within cluster, period-varying random effects to allow for differences between hospitals from baseline to follow-up, and admission-level random effects to account for correlation within person and hospital. Analyses of the baseline data, performed before randomization, found no evidence of overdispersion in a Poisson model, and so we plan to use that model for analysis of outcomes. The model can be expressed as follows:

$$log(y_{ijph}) = \beta_0 + \beta_1 A_{ijph} + \beta_2 T_{ijph} + \beta_3 A_{ijph} T_{ijph} + b_{0h} + b_{1h} T_{ijph} + g_i$$

where y_{ijph} is the ES-DOT per at-risk day for patient i for admission j in period p at hospital h, and $A_{ijph}=1$ if hospital h is in the intervention arm and 0 if not, and $T_{ijph}=1$ if p is the intervention period and 0 if baseline period. The random effects b_{0h} and b_{1h} allow for different baseline mean admission-level ES-DOT per at-risk day for each hospital and each hospital per period, respectively, while g_j allows different admissions to have different mean ES-DOT per at-risk day across multiple admissions. Equivalently, they allow for correlation within hospital at different levels at baseline and at follow-up.

The assessment of trial success will be determined by the significance of the arm by period interaction term β_3 , which assesses whether the log relative rate of the outcome due to being in the intervention arm in the intervention period is different from 0. The exponentiated parameter estimate for β_3 is the estimated relative rate of ES-DOT per at-risk day due to the intervention, relative to the baseline period. For example, if β_3 had a negative value and a p-value <0.05, we would conclude that the patient-specific CPOE smart prompts generated a benefit over routine care. Exponentiating the parameter value would provides an estimate of the relative reduction due to the intervention in the expected ES-DOT per at-risk day.

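### The safety outcomes are to be tested for non-inferiority with no margin, in a paragraph whose purpose and conservatism claim fit only a test for harm

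*SAP*

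**What the plan says.** The three safety outcomes are antibacterial escalation, ICU transfer and length of stay (SAP Table 2, Protocol Table 4). The safety paragraph of the SAP, under Primary Statistical Analysis, makes three statements that matter here; Protocol B.1.10 carries the same text.

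- Purpose: the outcomes "will be assessed in the most conservative manner to identify potential safety issues". The harm in view is that extended-spectrum drugs are withheld from patients who need them.
- Test: "Each safety outcome will be evaluated for non-inferiority using an as-randomized unadjusted model with a one-tailed significance set at alpha = 0.05". The model is a proportional hazards model with hospital random effects.
- Multiplicity: "Because these are safety outcomes, we do not intend to make adjustments for multiple comparisons in testing them, further increasing conservatism".

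Neither document mentions non-inferiority anywhere else. Neither gives a margin, a null value, a confidence-bound rule or a rule for combining the three results. The power tables (SAP Table 4, Protocol Table 5) cover the primary and secondary outcomes only.

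**The concern.** A non-inferiority test asks whether the hazard ratio is shown to lie inside a stated margin. Without a margin there is nothing to test against. The rest of the paragraph describes a different test, one that looks for harm against a hazard ratio of 1. The two have opposite error structures. In a harm test, rejection means harm was found and a type I error is a false alarm. In a non-inferiority test, rejection means the intervention is not unacceptably worse and a type I error is a false safety claim. The statement that leaving out adjustment adds caution can be true only of the first.

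At stake is the plan's own check on the harm it names. As the text stands, a harm test that fails to reach significance could be reported as demonstrated non-inferiority, and nothing pre-specified would contradict that report. The wording also leaves room for a margin to be set after the arms have been compared.

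**Working it through.** There is no safety sample size, event count or power figure in the documents to reproduce. The inputs are three outcomes (SAP Table 2) and one-tailed 0.05 for each, unadjusted (SAP Primary Statistical Analysis, Protocol B.1.10). Margins, standard errors (SE) and correlations below are assumptions for illustration, not proposals. Hazard ratios (HR) are oriented so that a value above 1 is harmful; for time to discharge the ratio is inverted.

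**1. The two readings as tests.**
- Harm: null HR ≤ 1; reject if ln(HR)/SE > 1.645. This can be run from the text.
- Non-inferiority: null HR ≥ M; reject if ln(HR) + 1.645 × SE < ln(M). This cannot be run, because M is missing. Setting M = 1 turns it into a superiority test, which a truly neutral intervention would pass 5% of the time per outcome.

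**2. What leaving out adjustment does under non-inferiority.** Take the worst case: all three outcomes exactly at their margins, each claimed separately. No margin or SE is needed. With independent statistics:
- unadjusted: 1 − (1 − 0.05)³ = 0.1426
- at 0.05/3: 1 − (1 − 0.0167)³ = 0.0492

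For equally correlated normal statistics, the probability of at least one rejection is 1 − ∫ Φ((z − √ρ·u)/√(1 − ρ))³ φ(u) du, with z = 1.645 or 2.128:

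| Assumed ρ | Unadjusted 0.05 | 0.05/3 per test | Ratio |
|---|---|---|---|
| 0 | 14.3% | 4.9% | 2.90 |
| 0.3 | 13.0% | 4.6% | 2.81 |
| 0.6 | 11.1% | 4.1% | 2.74 |

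Each single test keeps its 5%. If all three must pass before safety is claimed, the overall error is at most 5% without adjustment. Omission is then harmless, but it still adds no caution.

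**3. What the same choice does in a harm test.** The chance of missing a true HR of 1.10 on one outcome is Φ(z − ln(1.10)/SE), with ln(1.10) = 0.0953:

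| Assumed SE of ln(HR) | Unadjusted (z = 1.645) | Adjusted (z = 2.128) |
|---|---|---|
| 0.03 | 6% | 15% |
| 0.05 | 40% | 59% |
| 0.10 | 76% | 88% |

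Here leaving out adjustment lowers the chance of missing harm, so the conservatism claim is correct under this reading.

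**4. A null harm test read as non-inferiority.** With an assumed margin of 1.10, the unadjusted column in step 3 is also the chance that an outcome truly at the margin would be called safe: 6%, 40% or 76%, where a proper non-inferiority test would give 5%. The rate is held to 5% only if SE ≤ ln(1.10)/(2 × 1.645) = 0.029.

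**5. The two tests can disagree on the same data.**
- HR 1.05, SE 0.04: harm p = 0.11, no signal. The one-sided 95% upper bound is 1.12, which fails a margin of 1.10 and meets one of 1.20.
- HR 1.03, SE 0.015: harm p = 0.024, a signal. The upper bound is 1.056, which meets a margin of 1.10.

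**The case against.** The strongest reply is that a harm test was plainly meant. The purpose, the one-sided level and the multiplicity remark all fit it, and on that reading the analysis can be run with only one term out of place. This is largely fair, and it is why a wording change is enough. It does not remove the problem, because the out-of-place term sits in the only sentence that names the test, and step 5 shows that the choice can change the reported conclusion.

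A second reply is that familywise control across separate safety claims is a matter of preference, and that the 14.3% is a worst case. That also stands. The objection here is not that adjustment is required, but that the property claimed for omitting it is false under the named test.

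The consequences are also limited. These are other pre-specified outcomes. According to the SAP, "Safety outcomes will be analyzed separately from the main effectiveness outcomes of the trial". For the primary outcome, "The assessment of trial success will be determined by the significance of the arm by period interaction term".

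A reader might infer more from the fact that the safety paragraph does not say which hazard ratio is tested, and conclude that no margin could be interpreted. The documents do not support that. Hospitals are randomized, so the arm-by-period interaction and the intervention-period arm contrast aim at essentially the same effect and differ mainly in precision and in how chance baseline imbalance is handled. Protocol B.1.1 and B.1.6 also lean toward the comparison with baseline. Naming the term is a clarification.

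A reader might likewise try to bound the safety SE from the number of hospitals. The 59 units belong to the power simulation, the recruitment target in Protocol B.1.3 is at least 40 facilities, and Protocol B.1.5 plans to balance length of stay and ICU transfers, so no firm bound follows.

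**Conclusion.** The point holds as an internal contradiction that should be fixed. The named test lacks a margin in both documents, and the paragraph claims a property that only the other test has. Under non-inferiority, omitting adjustment multiplies the worst-case chance of at least one false safety claim by about 2.7 to 2.9 if the outcomes are claimed separately, and is neutral if all three must pass. That result rests only on three tests at 0.05, all outcomes at their margins and the assumed correlations. The 6%, 40% and 76% figures depend on an assumed margin and assumed SEs, and show the direction of the risk rather than its size in this trial.

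The documents do not show that a margin was or will be chosen after the fact, nor that the safety analysis cannot be carried out at all; a reader might infer either, but the text shows only that both routes are left open. The primary ES-DOT conclusion is unaffected.

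**What to change.** Amend the safety paragraph in the SAP and in Protocol B.1.10 before the arms are compared, in one of two ways.

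**Preferred: harm test.** Replace the non-inferiority wording with a one-sided test for harm, null hazard ratio 1. Keep 0.05 unadjusted. Report each hazard ratio with its two-sided 90% confidence interval, which matches the one-sided level. State that a non-significant result does not show safety. The change is to wording only. Its price is that the trial cannot then claim safety was shown.

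**Alternative: non-inferiority.** Pre-specify and justify a margin for each outcome. Remove only the closing clause about conservatism, because the rest of that sentence is the sole multiplicity rule for the safety outcomes. State that rule fully: either all three must pass, or each claim stands alone with its unadjusted 5% acknowledged. This takes the work of justifying three margins, and since the documents give no safety event rates or safety power, precision may prove too low to meet them.

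**Under either option, as secondary clarifications,** name the hazard ratio (arm-by-period interaction or intervention-period contrast) and write down the direction of harm for each outcome. It is reversed for length of stay, defined as "Days from hospital admission to discharge", where a lower hazard is worse.
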